7.2.3. Duration of Event

Where the duration of an event is to be calculated, it will be derived as: (Event stop/end date – Event start date) + 1.

7.2.4. Treatment Period

- Pre-treatment period = Date of Screening to Date of first dose minus 1
- On-treatment period = Date of first dose to Date of last dose plus 28 days inclusive
- Post-treatment period = End of last dose plus 29 days to End of study date

7.2.5. OCS Dose Reduction

Percent OCS Dose Reduction during Weeks 20 - 24 = 100 * (Baseline Dose – Maintenance Dose during Weeks 20 - 24)/Baseline dose.

Baseline dose is defined as the prescribed optimized prednisone/prednisolone dose following the OCS optimization run-in period and maintenance dose is defined as the mean average of all daily prednisone/prednisolone doses during the maintenance phase of Weeks 20 -24. The visit window for calculating OCS dose at each reporting period is described below:

| Reporting Period | First Day Included | Last Day Included |
|--------------------------------------|-------------------------|----------------------|
| Optimised Dose | N/A | N/A |
| Baseline – Week 4 | Day after Week 0 visit | Day of Week 4 visit |
| Week 4 – Week 8 | Day after Week 4 visit | Day of Week 8 visit |
| Week 8 – Week 12 | Day after Week 8 visit | Day of Week 12 visit |
| Week 12 – Week 16 | Day after Week 12 visit | Day of Week 16 visit |
| Week 16 – Week 20 | Day after Week 16 visit | Day of Week 20 visit |
| Maintenance Dose (Week 20 – Week 24) | Day after Week 20 visit | Day of Week 24 visit |
| | - | - |

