4.1.2. Treatment period

At Visit 2 (Week 0), participants who meet the Treatment Period eligibility criteria will receive Mepolizumab 100mg SC every 4 weeks.

Subsequently, participants will continue to receive with mepolizumab 100mg SC every 4 weeks. During this period, participants will remain on their baseline asthma medications. OCS use and OCS dose adjustment in participants will be as per the investigator's discretion and clinical practice.

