4.2. Scientific Rationale for Study Design

Though safety and efficacy of mepolizumab in patients with severe eosinophilic asthma has been established in various clinical studies across USA and Europe, this will be the first clinical study to assess safety in Indian patients.

Eosinophilic inflammation of the airways plays a central role in the pathogenesis of asthma (Seminario, 1994; Rothenberg, 1998; Wardlaw, 2000; Cohn, 2004). The overproduction of IL-5 has been specifically reported in patients with a variety of eosinophil associated disorders including asthma (Robinson, 1992; Sur, 1995). Mepolizumab binds with high specificity and affinity to human interleukin 5 (IL-5), the key cytokine responsible for regulation of blood and tissue eosinophils. A therapeutic strategy targeting IL-5 with mepolizumab represents a focused therapeutic option, which results in reduced eosinophil levels and important clinical benefits for patients with eosinophilic inflammation associated with severe asthma who are receiving optimised standard of care therapy.

There is significant unmet medical need to provide better treatment options in patients with severe eosinophilic asthma who need systemic corticosteroids for maintenance, given undesirable safety profile of OCS and the limited application of omalizumab in severe asthma (Normansell, 2014). In patients aged ≥12 years with severe eosinophilic asthma in the phase III studies, adding subcutaneous mepolizumab 100 mg q4w to current asthma therapy significantly reduced the rate of clinically relevant asthma exacerbations and significantly improved asthma control and had acceptable tolerability (with headache the most common adverse event). Further, the SIRIUS study demonstrated that in patients requiring daily oral glucocorticoid therapy to maintain asthma control, mepolizumab had a significant glucocorticoid-sparing effect. This study will also evaluate the OCS sparing effect in Indian patients with severe eosinophilic asthma (only to be assessed in patients who completed or withdrew from the study prior to the adoption of protocol amendment 4).

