10.12. Appendix 12: Protocol Amendment History

The Protocol Amendment Summary of Changes Table for the current amendment is located directly before the Table of Contents (TOC).

Amendment 4 03-AUG-2022

Overall Rationale for the Amendment:

- i) The requirement of oral corticosteroids (OCS) and associated phases (Induction phase, optimization phase, OCS reduction/Manitenance phase) has been removed.
- ii) Inclusion criteria (S. no. 5) have been updated from the study to align with the current management practice of SEA which does not include use of stable OCS use for prolonged periods of time and the changes are in line with Prescribing information of the product.
- iii) Stringency of spirometry timings (i.e. must be performed at the same time ± 1 hour of the visit 1) has been removed.
- iv) The recommendation of triplicate 12-lead ECG within 4 minutes duration has been removed.
- v) The information for reporting SAE to GSK has been updated.

Amendment -3 17-MAR-2021

Overall Rationale for the Amendment:

i) As per recommendation by DCGI, Immunogenicity assessments have been added at Induction Phase, IP discontinuation Visit/End of Study Visit. Details of Immunogenicity testing provided

Amendment 2 05-NOV-2020

Overall Rationale for the Amendment:

- i) The time point for IgE (total) are updated and testing for IgE (specific) is removed.
- ii) The immunogenicity testing is no longer applicable for this study
- iii) Changes in the spirometry assessments are made.
- iv) Rescreened patients will be assigned a new screening number.
- v) The guidance to conduct the study during COVID-19 pandemic is added.

Amendment 1 27-AUG-2019

Overall Rationale for the Amendment:

- i) The sample size revised to 100 evaluable patients
- (ii) In the inclusion criteria, the age of the patients to be enrolled is \geq 18 years
- (iii) IgE levels evaluated before screening of patients

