6.2. SAFETY POPULATION

All participants who take at least 1 dose of study intervention. This population will be used for all safety, efficacy and health outcomes.

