10.7. IMPUTATION OF MISSING DATA

Missing values will be treated as missing unless and otherwise specified. If a subject experience a clinically significant asthma exacerbation between Weeks 20-24, then for the purpose of assessing percentage of subjects achieving at least 50% reduction in OCS dose during the weeks 20-24, the subject will be imputed into the worst-case category of 'no reduction in OCS Dose'. For the analysis of median percent OCS reduction during weeks 20-24, the subject will be imputed using the maximum dose of OCS observed during the 4-Weekly period across all participating subjects.

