APPENDIX 5. LIST OF TABLES, FIGURES AND LISTINGS

List of Tables

| Table | Table Title |
|-----------|--|
| Number | |
| 14.1.1.1 | Summary of Subject Disposition (Enrolled Population) |
| 14.1.1.2 | Summary of Reasons for Discontinuation (Safety Population) |
| 14.1.1.3 | Summary of Reasons for Screen or Run-in Failure (All Enrolled Population) |
| 14.1.1.4 | Summary of Inclusion, Exclusion and Induction Phase Criteria Deviations (Safety Population) |
| 14.1.1.5 | Summary of Important Protocol Deviations (Safety Population) |
| 14.1.1.6 | Summary of Important Protocol Deviations Leading to Exclusion to Treatment (Safety Population) |
| 14.1.1.7 | Summary of Important Protocol Deviations Related to COVID-19 Pandemic (Safety Population) |
| 14.1.1.8 | Summary of Visits Impacted by COVID-19 Pandemic (Safety Population) |
| 14.1.2.1 | Summary of Demographic Characteristics (Safety Population) |
| 14.1.2.2 | Summary of Asthma History and Baseline Disease Characteristics (Safety Population) |
| 14.1.2.3 | Summary of Asthma Exacerbation History (Safety Population) |
| 14.1.2.4 | Summary of Family History of Cardiovascular Risk Factors (Safety Population) |
| 14.1.2.5 | Summary of Medical Conditions (Safety Population) |
| 14.1.2.6 | Summary of Asthma Medications Taken by Treatment Period and Respiratory Medication Class |
| | (Safety Population) |
| 14.1.2.7 | Summary of Non-Asthma Concomitant Medications Taken During Treatment (Safety Population) |
| 14.1.2.8 | Summary of Screening, Run-in and Baseline Lung Function Results (Safety Population) |
| 14.1.3 | Summary of Treatment Exposure and Number of Study Drug Administration (Safety Population) |
| 14.2.1.1 | Analysis of Subject Achieved at least 50% Reduction in OCS Dose During Weeks 20-24 |
| 44.0.4.0 | Relative to Baseline, while Maintaining Asthma Control (Safety Population) |
| 14.2.1.2 | Summary of OCS Dose Categories During Weeks 20-24 (5 mg Cut-off) (Safety Population) |
| 14.2.1.3 | Summary of OCS Dose Category During Each Reporting Period (Safety Population) |
| 14.2.1.4 | Summary of Percent Change from Baseline OCS Dose Categories Relative to Baseline by Reporting Period (Safety Population) |
| 14.2.1.5 | Summary of OCS Dose (mg/day) and Change from Baseline During Each Reporting Period (Safety Population) |
| 14.2.1.6. | Summary of Median Percent OCS Dose (mg/day) Reduction During Weeks 20-24 While |
| | Maintaining Asthma Control (Safety Population) |

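### The visible SAP plans the exploratory OCS-reduction outputs in the Safety Population, although Protocol 4.2 limits that assessment to a pre-Amendment 4 subset; separately, it plans a Week 24 IgE table for which no sample is scheduled

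*SAP*

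**What the plan says.** **OCS, protocol.** Protocol 4.2 says that the OCS-sparing effect is "only to be assessed in patients who completed or withdrew from the study prior to the adoption of protocol amendment 4". This is current text, not an entry in the amendment log. Under the present design there is no protocol-driven OCS schedule. Protocol 4.1.2 reads "OCS use and OCS dose adjustment in participants will be as per the" and leaves the matter to the investigator. Appendix 12 records that the OCS requirement and its "associated phases (Induction phase, optimization phase, OCS reduction/Manitenance phase) has been removed".

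**OCS, SAP.**
- SAP 7.2.5: "Baseline dose is defined as the prescribed optimized prednisone/prednisolone dose following the OCS optimization run-in period". Percent reduction is measured against that dose.
- SAP 6 has two populations, Enrolled and Safety. The latter is "All participants who take at least 1 dose of study intervention".
- SAP Appendix 5 titles every OCS-reduction table Safety Population, for example Table 14.2.1.4: "Summary of Percent Change from Baseline OCS Dose Categories Relative to Baseline by Reporting Period (Safety Population". Table 14.2.1.2 is "Summary of OCS Dose Categories During Weeks 20-24 (5 mg Cut-off) (Safety Population").
- SAP 10.7 has two rules for a participant with a clinically significant exacerbation in Weeks 20-24. For the analysis of at least 50% reduction, the participant is put in the no-reduction category. For the median percent reduction, "the subject will be imputed using the maximum dose of OCS observed during the 4-Weekly period across all participating subjects".
- The only visible subgroup (SAP 10 and 10.5) is baseline OCS use, yes or no.

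**IgE.** SAP 10.4 plans a repeated-measures model of the total IgE ratio to baseline at each scheduled visit, and Table 14.2.8.10 reports it at Week 24 in the Safety Population. The Schedule of Activities (Protocol 1.3) and SAP 11.3 both list IgE at pre-screen, screening and Week 0 only.

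**The concern.** The SAP is written against Amendment 4, yet its visible OCS definitions belong to the earlier design, and nothing visible ties them to the participants for whom the protocol still allows the assessment. A programmer working from these sections could put participants whom Protocol 4.2 excludes into the OCS-reduction tables. The titles would not reveal it, and the number in the protocol's subset would not be shown. Baseline OCS use is no substitute for that subset, because a participant enrolled under the current design can also be on OCS at baseline.

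The IgE problem has the same origin. A Week 24 result could rest only on participants sampled under an earlier protocol version while carrying a whole-population title.

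**Working it through.** The plan gives no figure on this point to reproduce, and it does not give the size of the subset. The check is therefore a comparison of the rules, followed by a bound.

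**1. Who is kept out of the OCS-reduction outputs?** SAP 7.2.5 computes

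percent reduction = 100 × (baseline dose − Weeks 20-24 dose) / baseline dose,

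which does not exist without a run-in dose. SAP 12 takes participants with an observation as the default percentage denominator. Applying both:

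| Participant | Protocol 4.2 | Run-in dose | Kept out by the visible SAP? |
|---|---|---|---|
| Finished or left before adoption | Included | Expected | Not applicable |
| Enrolled under an earlier version, on study at adoption | Excluded | Possible | No |
| Enrolled under Amendment 4, no Weeks 20-24 exacerbation | Excluded | None | Yes: no baseline, so no observation |
| Enrolled under Amendment 4, Weeks 20-24 exacerbation | Excluded | None | Tables 14.2.1.4, 14.2.1.5 (change) and 14.2.1.6: yes. Table 14.2.1.1: not on a literal reading, because SAP 10.7 assigns a category without asking for a baseline dose |

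In Table 14.2.1.1 the last group could enter only as failures, so that leak runs in one direction.

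**2. How far could that move Table 14.2.1.1?** Let the subset contribute m participants with r responders, and let f later participants be added by SAP 10.7. The percentage goes from 100 × r/m to 100 × r/(m + f). Neither m, r nor f is in the documents. As an assumption, take half the subset as responders and 100 treated:
- m = 50, r = 25: from 25/50 = 50% (f = 0) to 25/100 = 25% (f = 50).
- m = 10, r = 5: from 5/10 = 50% (f = 0) to 5/100 = 5% (f = 90).

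The lower ends need every other treated participant to be a later enrollee with an exacerbation in Weeks 20-24. They are outer bounds, not estimates.

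**3. The maximum-dose rule.** The maximum is taken over all participating subjects, so the value given to a subset member could come from someone outside the subset. It feeds a median (Table 14.2.1.6), which changes only if the imputed value carries a participant's rank across the middle. The effect may be nil.

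**4. IgE.** The post-dose visits are Weeks 4, 8, 12, 16, 20 and 24. IgE is scheduled at 0 of these 6, in both the Schedule of Activities and SAP 11.3. SAP 7.2.2 sets baseline at Visit 1, which leaves Week 0, the first-dose visit, as the only scheduled value after baseline. Week 24 values can come only from samples outside the current schedule.

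**The case against.** **Redaction.** The exploratory objectives in Protocol 3 and SAP 3.3 and the endpoint list in SAP 10.1.3 are blank, and no visible section gives the method for Table 14.2.1.1. A subset rule would naturally sit there. This stands. A reader might infer that the SAP omits the restriction altogether, and the documents do not support that. What can be said is that the visible SAP 6, 7.2.5, 10.7 and table titles do not match Protocol 4.2.

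**Precedence.** SAP 2 lets the SAP supersede the protocol where it describes a difference. It also says that such changes are set out in the SAP, and no visible passage presents this as one. SAP 5.4, 9.1 and 11.1 still refer to an induction phase, which suggests carried-over text rather than a decision.

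**Self-limiting definitions.** The run-in baseline and the SAP 12 denominator do most of the work, and SAP 12 leaves denominator details to footnotes. This largely stands. A reader might infer that all 100 treated participants enter the denominator and that the responder rate is diluted accordingly. The denominator rule does not support that; only the two groups identified above remain exposed, and their number could be zero.

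**Descriptive outputs.** Protocol 4.2 limits the assessment of sparing, not every description of OCS dose, and daily dose is still recorded (Protocol 8.1.4). This stands. It would be wrong to treat every OCS output titled Safety Population as an error.

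**IgE.** The protocol's summary of changes shows that Week 24 IgE was once scheduled, so some values may exist, and SAP 10.4 already reports numbers of subjects in the descriptive summary. The table need not be empty, as a reader might infer. The conflict between the SAP's own schedule and its Week 24 table remains.

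**Conclusion.** The concern holds in a limited form. On the visible text, the OCS-reduction outputs (Tables 14.2.1.1, 14.2.1.4, the change-from-baseline part of 14.2.1.5, and 14.2.1.6) are assigned to a wider population than Protocol 4.2 allows, with two routes by which excluded participants could enter. Separately, the Week 24 IgE analysis conflicts with the sampling schedule in both documents.

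The actual effect is unknown, because the documents do not give the number who finished or left before adoption, the number with an optimised dose, or the proportion with a Weeks 20-24 exacerbation. The OCS conclusion assumes that the redacted text does not already hold the restriction, and the second route assumes that SAP 10.7 is programmed literally. Every affected output is exploratory; the primary safety analysis and the secondary efficacy analyses are untouched. It is worth correcting before database lock, as a matter of definition and labelling.

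**What to change.** **OCS.**
- In SAP 6, define the subset exactly as Protocol 4.2 does, with no added condition. Report its N and, within it, the n with an optimised baseline dose.
- Use it for Tables 14.2.1.1, 14.2.1.4 and 14.2.1.6 and for the change-from-baseline part of 14.2.1.5.
- Apply both SAP 10.7 rules only within the subset, and take the maximum dose from it.
- Table 14.2.1.2, Table 14.2.1.3, the actual doses in 14.2.1.5 and Figure 14.4.1.2 may stay in the Safety Population if labelled as observed dose. If Table 14.2.1.2 is offered as evidence of OCS sparing, use the subset.
- If redacted text already holds the restriction, align SAP 6, SAP 10.7 and the table titles with it.

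**IgE.** Delete the post-baseline model and Table 14.2.8.10. Otherwise, restrict both to participants with a Week 24 sample taken under an earlier protocol version, say so in the title, and show n.

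**Cost.** One population definition, some retitled tables, and one IgE table dropped or relabelled. No new data are needed. The price is a smaller N and wider intervals in exploratory tables.

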7.2.6. Asthma Exacerbations

For the analysis of exacerbations, the exacerbation follow-up time is defined as:

- For subjects completed the study: Date of Week 24 visit Date of Baseline (Week 0) visit +1
- For subjects with early withdrawals: Date of Withdrawal Date of Baseline (Week 0) visit + 1

The on-treatment assessment period for exacerbations is calculated from date of Baseline (Week 0) visit to date of Week 24 visit or early withdrawal (inclusive).

7.2.7. Concomitant Medication Derivation

Taken Before the Run-In: If medication start date < Date of Screening visit (Visit 1) (or medication start date is missing)

Run-In Period Medications:

- Medication start date < date of Screening visit (Visit 1) (or medication start date is missing) and medication stop date ≥ date of Screening visit (or medication stop date is missing), or
- Date of Screening visit ≤ medication start date < Date of first dose of study drug

On-Treatment Medications:

- Medication start date < date of first dose of study drug (or medication start date is missing) and medication stop date ≥ date of first dose of study drug (or medication stop date is missing), or
- Date of first dose of study drug < medication start date < date of last dose of study drug + 28 days
- Date of last dose of study drug is missing and the medication start date is on or after the date of first dose of study drug
- Medication start or stop date is missing or partial then the con-med will be considered on-treatment unless there is evidence to the contrary (e.g. month/year of con-med stop date is present and is before the month/year of study treatment start date).

Post-Treatment Medications:

- Medication start date is after the date of last dose of study drug + 28 days
- Medication stop date > date of last dose of study drug + 28 days or medication stop date is missing

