HBsAg and hepatitis C antibody		х									Hepatitis B Antigen and Hepatitis C antibody (if hepatitis C antibody positive, a hepatitis C RIBA immunoblot assay should be reflexively performed on the serum sample to confirm the result)
Serum IgE (total)	X	х	х								Serum IgE (Total) can be evaluated either at Pre-Screen visit i.e. before screening of patients (prior to Visit 1) or on the same day as ScreeningVisit 1.

Procedure	Pre- Screen	Screenin g		Treatment Period (visit window is ± 7days)					IP Discontinu ation visit	End of study visit	Notes
Visit		1	2	3	4	5	6	7		8	
Week		-2 to -1	0	4	8	12	16	20	4 weeks post last dose ± 7 days	24 or Early Withd rawal	
Immunogenicity Assessments			x						х	х	Serum sample will be collected at end of study visit OR at IP discontinuation visit. Sample collection to happen at 4 weeks from last dose of mepolizumab or at patient's last visit in case patient discontinues from the study
Investigational Product	t (IP)	1	T	1	T			1	T		
Administer IP			X	X	X	X	X	X			
Oral Corticosteroids dispensed (as needed)		X	Х	X	X	X	X	X			
Salbutamol dispensed (as needed)		x	X	X	X	X	X	X			
Collect dispensed salbutamol as needed			х	Х	Х	Х	Х	Х	Х	Х	
eCRF	1		1	1	1				1		
Complete eCRF		X	X	X	X	X	X	X	X	X	
Dispense paper worksheets		X	X	X	X	X	X	X	X		
Dispense eDiary and PEF meter		X									
Collect eDiary and PEF meter										X	
Collect/review paper worksheets			X	X	Х	Х	Х	X	X	Х	

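### The SAP's on-treatment rule for medications leaves out both boundary days, which its own on-treatment period includes, so some medications with complete dates drop out of the on-treatment tables

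*SAP*

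**What the plan says.** SAP 7.2.4 sets the study's treatment periods: "On-treatment period = Date of first dose to Date of last dose plus 28 days inclusive". Both end days belong to the period.

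SAP 7.2.7 then assigns each medication to periods by its own dates. The bullets that matter are:

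- Run-in, for a start on or after screening: "Date of Screening visit ≤ medication start date < Date of first dose of study drug".
- On-treatment bullet 1, for medications already in use: "Medication start date < date of first dose of study drug (or medication start date is missing"), with a stop date that is missing or not before the first dose.
- On-treatment bullet 2, for medications begun during treatment: "Date of first dose of study drug < medication start date < date of last dose of study drug + 28 days".
- On-treatment bullet 3, used only when the last-dose date is missing: "the medication start date is on or after the date of first dose of study drug".
- On-treatment bullet 4, the default: "Medication start or stop date is missing or partial then the con-med will be considered on-treatment unless there is evidence to the contrary".
- Post-treatment: a start after last dose plus 28 days, or "Medication stop date > date of last dose of study drug + 28 days or medication stop date is missing".

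Appendix 1 adds that an ongoing treatment gets no imputed stop date, and that a medication with no stop date at all counts as concomitant.

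**The concern.** Bullet 2 is the only route to on-treatment status for a medication begun during treatment when its dates are complete and the last-dose date is known. If that bullet excludes the two days that 7.2.4 includes, starts on those days have no route in.

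Both are nominally visit days. The first-dose day is Visit 2, where the Schedule of Activities marks "Oral Corticosteroids dispensed (as needed"), along with salbutamol. Last dose plus 28 days is nominally the Week 24 visit, four weeks after the Week 20 dose.

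What is at stake is the count of on-treatment medication use. SAP 9.3 tabulates asthma medications by treatment period and non-asthma medications for the on-treatment period only.

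**Working it through.** No sample size or error rate is involved, and the plan gives no figure to reproduce. The check applies the 7.2.7 rules to test records.

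**Notation.** F is the first-dose date, L the last-dose date, S the medication start and E its stop. The bullets within each category are read as alternatives.

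**Test days (assumed, nominal schedule).** Screening is Day -7, F is Day 1 and L is Day 141, so L + 28 = 141 + 28 = Day 169.

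**A start on the first-dose day, complete dates, L known (S = F = 1).**

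1. Before the run-in, and the first run-in bullet: these need S before screening or missing. Not met.
2. Second run-in bullet: S < F becomes 1 < 1. False.
3. On-treatment bullet 1: S < F. False.
4. On-treatment bullet 2: F < S < L + 28 becomes 1 < 1 < 169. False at the left-hand sign.
5. Bullet 3 needs L missing, and bullet 4 needs a missing or partial date. Neither applies.
6. Post-treatment: met only if E > 169.

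**A start on L + 28 (S = 169).** Bullet 2 becomes 1 < 169 < 169, which is false at the right-hand sign. The post-treatment start bullet, 169 > 169, is also false. Only a stop after Day 169 gives the record a category.

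**Results.** The last column changes bullet 2 to F ≤ S ≤ L + 28 and nothing else.

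| Start, stop | As printed | Bullet 2 inclusive |
|---|---|---|
| Day 1, Day 10 | no category | on |
| Day 1, Day 169 | no category | on |
| Day 1, Day 180 | post only | on and post |
| Day 1, ongoing | on (bullet 4) and post | on and post |
| Day 2, Day 10 | on | on |
| Day -1, Day 10 | run-in and on | run-in and on |
| Day 168, Day 169 | on | on |
| Day 169, Day 169 | no category | on |
| Day 169, Day 176 | post only | on and post |
| Day 169, ongoing | on (bullet 4) and post | on and post |

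If L is missing, the Day 1 to Day 10 record is on-treatment through bullet 3, and the change does not affect it.

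The failures are therefore confined to complete-dated starts on Day 1 or Day 169. Starts one day inside either boundary are classified correctly. The inclusive version puts every tested boundary record in the on-treatment period and leaves the other records as they were.

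**Partial dates.** Appendix 1 imputes a start date with a missing day, in the month of first dose, to the first-dose day itself, which is the day bullet 2 omits. Bullet 4 keeps such a record on-treatment if it is applied to the date as collected. The SAP does not state the order of the two steps, so these records are not counted here as misclassified.

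**The case against.** Four things can fairly be said for the plan.

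**The intended meaning is clear.** SAP 7.2.4 is inclusive, and so is bullet 3 of the same rule. This looks like a drafting slip rather than a choice. That stands and keeps the point minor. It does not remove it, because a program written from the printed inequality reproduces the gap.

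**Starts on these days may be few.** Oral corticosteroids and salbutamol are marked as dispensed when needed at every visit from Visit 1 to Visit 7, and dispensing is not a start date. Background medications begun before the first dose and continuing are captured by bullet 1. This also stands: the documents give no basis for calling Day 1 starts common.

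**The printed signs may not be the original ones.** Minus signs have been lost in the neighbouring SAP 7.2.6, so a lost bar under an inequality sign cannot be fully excluded. However, ≤ and ≥ survive elsewhere in 7.2.7, including in the run-in rule. An extraction fault is possible but not shown.

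**Little else depends on the rule.** A reader might infer that missing on-treatment corticosteroid records would distort how FEV1, ACQ-5 or exacerbation changes are interpreted. The documents do not support that:

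- Daily oral corticosteroid dose is recorded in the eDiary (Protocol 8.1.4). It is handled by its own reporting windows (SAP 7.2.5) and conversion factors (SAP Appendix 2), and reported in Tables 14.2.1.2 to 14.2.1.5.
- The FEV1, ACQ-5 and PEF models adjust for baseline maintenance use (SAP 10.2.2 to 10.2.4).
- Exacerbation follow-up has its own inclusive window (SAP 7.2.6).
- On-treatment adverse events have their own inclusive definition (SAP 4 and 11.2).

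**Conclusion.** Wrong as written, at minor severity. SAP 7.2.7 and 7.2.4 contradict each other on two days, and the contradiction leaves some complete-dated records out of the on-treatment period, or out of every period.

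A reader might go further and infer that an ongoing medication started on the first-dose day would be classed as post-treatment only. It would not. An ongoing medication has no stop date, so bullet 4 makes it on-treatment and Appendix 1 calls it concomitant; the post-treatment rule then counts it there as well. Post-treatment only is the result just for a boundary-day start with a recorded stop later than last dose plus 28 days.

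The counts affected are in Table 14.1.2.6 (asthma medications by period) and Table 14.1.2.7 (non-asthma concomitant medications). The number of records is not given and cannot be derived from the documents. The records themselves are not lost, since SAP 9.3 also provides by-subject listings of all asthma and non-asthma medications.

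The conclusion assumes that the signs are as printed, that the bullets within each category are alternatives, and that bullet 4 is applied to dates as collected.

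**What to change.** In SAP 7.2.7, change on-treatment bullet 2 to: date of first dose ≤ medication start date ≤ date of last dose + 28 days. This matches 7.2.4 and needs no change to the other bullets.

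While editing, add one sentence stating whether bullet 4 is applied before or after the Appendix 1 date imputation. Check also which rule assigns the period in Listing 16.2.6.1 (oral corticosteroid therapy by treatment period), since the SAP does not say.

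The cost is two comparison signs in the SAP and the matching line in the program, with a rerun of the two medication tables if they already exist. No new data are needed, and the design and the other analyses are unaffected.
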